Below, we propose a sequential 2-level dose escalation study of the safety, pharmacokinetics (drug concentration over time) and pharmacodynamics (i.e., muscle strength response) of lorcaserin in critically ill patients with muscle weakness. We selected two different one-time doses of the study drug to provide dose-response data over a range of doses deemed safe for the ICU setting. As described above, these doses are anticipated to bracket (i.e., fall above and below) the anticipated effective dose based on preclinical studies and established differences between species. Observations for drug effect on muscle weakness, adverse events, and drug concentration will be made at specified intervals after each dose (as outlined below). The time between doses, 48 hours, was selected to provide time for the anticipated drug concentrations and muscle strength effects to return to baseline before the second, higher dose

4) Study Procedures

4-a) Study design, including the sequence and timing of study procedures (distinguish research procedures from those that are part of routine care).

Potentially eligible participants will be identified through screening of the Johns Hopkins Hospital's medical and surgical ICU census (see section 5 for specific eligibility criteria) and IRB approved medical floors under a HIPAA waiver. We will be engaging the CCDA to develop and provide us a daily report of patients on our IRB approved floors who were screened by a treating provider for sepsis and the results of this sepsis screen. Daily reports would be sent to the SAFE virtual desktop. Members of research team who are on this protocol will then review the charts of these patients who had a positive sepsis screen to determine if they meet other inclusion criteria and do not meet exclusion criteria. Potential eligibility will be confirmed by the research team with the patient's attending physician. A treating provider will obtain permission from the patient or surrogate to approach them for a discussion about possible participation in the study.

4-a-1) Informed Consent

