Informed consent will be sought for completion of the study eligibility screening and for participation in the study via oral and written consent respectively. Some patients may be incapable of providing informed consent. In such cases, informed consent will be obtained from their surrogate decision-maker. Surrogate decision-makers will be identified as the individual who is making decisions on behalf of the patient for clinical care in the ICU. Consent will be obtained in two steps. First, oral consent will be obtained to perform a brief (< 5 minute) in-bed assessment of muscle strength using a standardized protocol to determine eligibility. Only those patients who are weak, defined either by (a) composite muscle strength sum-score, using Medical Research Council (MRC) scale, <48/60, or (b) a handgrip strength of <11 kg in men and <7 kg in women(2), will be offered written informed consent (since demonstrated muscle weakness is an entry criteria). During the written informed consent process details on the intent of the proposed study, its design, the type of information collected, and potential risks and benefits of participation will be discussed. If surrogates were consented because of the patient's incapability, we will monitor the patient for return of capability and once they are capable, acquire consent from them for continuation in the study.

4-a-2) Planned flow of participants through the study

After consent is obtained, a chart review will be performed to ensure patient still meets eligibility and safety criteria (sections 5 and 4-f, respectively).

4-a-3) Randomization

After informed consent is obtained, eligible patients will be randomly assigned in a 2:1 ratio to the intervention (lorcaserin) or control group (placebo) respectively. (Please see Table 3 and section 4-a-6 for detailed study events.) Group assignment will be masked for patients, clinical and research staff administering the lorcaserin/placebo, and assessing outcomes (muscle strength, safety outcomes, or serum sample collection), as discussed under section 4-c.

4-a-4) Measurement of Exposures and Potential Confounders:

Patient exposures and potential confounders will be collected at study enrollment and are outlined in Table 1. Table 2 summarizes ICU-related exposures and possible confounders that will be collected during the study.

Table 1: Patient-related exposures and potential confounders – Baseline status

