Patient Risk Factors	Method for data collection	Measurement Scale
Age/sex/race/ethnicity	Chart review	Continuous/Binary/Categorical
Weight/Height	Chart review	Continuous
Comorbidities: Charlson* & Functional Indices**	Chart review	Ordinal
Severity of illness: APACHE II***	Chart review	Continuous
Leg/Hand dominance	Patient/Proxy interview	Binary
Past Psychiatric History***	Chart review	Categorical

*Charlson Comorbidity index: a score derived from 19 categories of comorbidities, with an increased score reflecting an increased likelihood of one-year mortality(20).

**Functional Comorbidity Index: An 18 item list of diagnoses which uses physical function as the outcome of interest, with increased score indicative of decreased function(21).

Date: 1 August 2016

Principal Investigator: [name] PhD

Application Number: IRB00072940

****Acute Physiology and Chronic Health Evaluation (APACHE II): An index of disease severity that takes into account age, pre-existing medical conditions, and 12 acute physiologic variables that are assessed during the first 24 hours of ICU admission. Scored on a scale from 0-71, with higher scores indicating more severe disease and increased mortality risk(22).*

Table 2: Potential confounders – ICU status

ICU exposure risk factors	Method of Data Collection	Measurement Scale
Sequential Organ Failure Assessment (SOFA) Score**	Chart review	Continuous
ICU admission diagnosis details	Chart review	Categorical

** *SOFA: A composite score that takes into account 6 organ systems used to assess the severity of organ dysfunction in ICU(23), collected on Days 1 and 3.*

4-a-5) Sequence and Timing of Study Events

On Day 1, intervention and control group participants receive 10 mg of lorcaserin or placebo, respectively. Both groups also will undergo assessments before and after administration of lorcaserin/placebo (for assessment details and times, see table 3 and section 4-a-6)

On Day 2, the intervention and control group participants will not receive any lorcaserin/placebo, but will undergo repeat assessments (for assessment details and times, see table 3 and section 4-a-6)

On Day 3, the intervention and control group participants receive 30 mg of lorcaserin or placebo, respectively. Both groups also will undergo assessments before and after administration of lorcaserin/placebo (identical to Day 1).

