‡ Peak concentration serum samples will be collected 2 hours ± 15 minutes or 3 hours ± 15 minutes after drug administration (see section 4-a-6.11 for details) and trough concentration serum samples will be collected 24 hour ± 30 minutes after drug administration (see section 4-a-6.11 for details)

† Days 2 and 4 are consecutive to days 1 and 3 respectively.

‡ Day 3 may or may not be consecutive to day 2 depending on assessor availability.

Safety Measures

4-a-6.1) *Chart Review*: A daily review of participants' medical records for interim medical history and medications will be performed to monitor for any safety issues and ensure that participants continue to meet eligibility and safety criteria (see sections 5 and 4-f respectively).

4-a-6.2) *Laboratory Tests*: As indicated in table 3 above, participants will undergo daily blood draws for the following standard laboratory tests: Heme 8 and CMP. In particular, laboratory tests will be obtained prior to every dose of lorcaserin or placebo to ensure that patients meet eligibility and safety criteria (see sections 5 and 4-f respectively). If the relevant tests have already been done for clinical purposes, they will NOT be repeated for research purposes. As these labs are typically measured, at least daily, in the ICU setting, they may not need to be drawn for research purposes and the pre-existing values will be reviewed for research purposes.

4-a-6.3) *EKG*: Daily EKGs will be obtained to determine if participants develop bradycardia, new-onset QT prolongation (as defined in Section 4.f.3.4 below) or new 2nd or 3rd degree AV block. In particular, this test will be obtained prior to every dose of lorcaserin or placebo to ensure that patients meet eligibility and safety criteria (see sections 5 and 4-f respectively). If this test has already been done for clinical purposes, it will NOT be repeated for research purposes. As this test is commonly done, at least daily, in the ICU setting, it may not need to be done for research purposes and the pre-existing test will be reviewed for research purposes.

Date: 1 August 2016

Principal Investigator: [name] PhD

Application Number: IRB00072940

4-a-6.4) Richmond Agitation Sedation Scale (RASS)(25): is a validated instrument to measure agitation and sedation status in ICU patients. Participants will be screened for their sedation status daily as well as pre- and post-drug or placebo administration as indicated in table 3 above.

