4-a-6.11) Serum Drug Levels: Daily blood samples will be collected to determine lorcaserin serum levels by a LC-MS/MS assay and pharmacokinetics. The serum drug samples will be collected and run in at least 2 batches, with the first batch run on specimens after randomization of at least the first 3 patients to lorcaserin (will be done without unblinding the research team regarding the study ID of these subjects). The peak plasma concentration after oral dosing is 1.5 to 2 hours. However, feeding can increase the peak plasma time by 1 hour. Thus, peak concentration samples will be collected at 2hours \pm 15 minutes for NPO patients and at 3 hours \pm 15 minutes for fed patients. Lorcaserin has a plasma half-life of about 11 hours, and trough concentration samples will be collected at approximately two half-lives, or 24 hours \pm 30 minutes.

4-a-6.12) Electromyography (EMG) and Nerve Conduction Studies (NCS):

Nerve conduction will be assessed via the following screening nerve conduction studies in participants after enrolment, to detect potential peripheral neuropathy. NCS results will help us interpret the results of strength tests.

- Motor NCS of bilateral peroneal nerves
- Motor NCS of unilateral ulnar nerve. If ulnar neuropathy at the elbow is diagnosed (slowing of ulnar conduction velocity across the elbow to below 35 m/s or a drop in ulnar motor amplitude of >50% with stimulation above the elbow), Motor NCS of the ulnar nerve of the other extremity will be performed as well.

- Sensory NCS of unilateral ulnar and sural nerves

Motor unit recruitment rate will be assessed via the following EMG studies as well

- EMG of unilateral vastus lateralis muscle
- EMG of unilateral deltoid muscle

If EMG and NCS studies have already been done for clinical purposes, they will NOT be repeated for research purposes, and the pre-existing results will be used for research purposes.

4-b) Study duration and number of study visits required of research participants.

Each participant regardless of group, will be in the study for two 2-day blocks. The detailed timeline of events are detailed in Table 3.

4-c) Blinding, including justification for blinding or not blinding the trial, if applicable.

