- 2) replication of the primary analysis excluding any patients with neuropathy based on nerve conduction studies (29) within the intervention group,
- 3) comparison of the change from baseline to post-drug testing across the 10 mg versus 30 mg conditions using a paired t-test
- 4) a PK-PD analysis for all concentration-strength measures for all observations (across the 4 days) using a traditional Emax model pooling all subjects and all time points.

7-c) Statistical plan including sample size justification and interim data analysis.

The sample size (N=10 for lorcaserin and N=5 for placebo) is a convenience sample to establish preliminary data for a potential larger future study. With $\alpha = 0.05$, power = 80%, and a mean (standard deviation) baseline value of 9 (9) kg for the primary outcome of grip strength, under a 30 mg dose of lorcaserin we could detect a difference of >9 kg for the change in strength from baseline to post-drug testing (on the same day) for the intervention group versus no change for the placebo group. This difference represents a 100% increase in strength versus a 400% increase detected with an equivalent dose in the rat model. This calculation assumes that the baseline and post-drug testing measures would be highly correlated ($r = 0.8$). Under a worst case scenario (i.e., no correlation between baseline and post-drug testing), we could detect at least a 220% increase in strength which is adequate given the large increase expected based on rat models.

7-d) Early stopping rules

There are no early stopping rules for this pilot trial.

8) Risks

8-a). Medical risks, listing all procedures, their major and minor risks and expected frequency.

1) Side effects of Drug / Placebo:

Participants will be closely monitored for any side effects related to administration of the study drug or placebo.

The placebo has no known side effects.

Date: 1 August 2016

Principal Investigator: [name] PhD

Application Number: IRB00072940

The study drug, lorcaserin, has been extensively studied, has an excellent safety profile and is FDA approved for chronic use for purposes of weight loss(19). The major potential side-effects are listed below. A full list of side effects is available in Appendix C, the FDA prescribing information.

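### The paired 10 mg versus 30 mg test (7-b item 3) estimates dose plus any day effect, because dose order is fixed; report the placebo-adjusted contrast and its interval beside it

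*Combined protocol and SAP*

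**What the plan says.** Section 7-b, item 3 of the combined protocol and SAP lists a "comparison of the change from baseline to post-drug testing across the 10 mg versus 30 mg conditions using a paired t-test". Only lorcaserin patients have both conditions, so the test uses that arm alone.

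Dose order is the same for everyone. Section 4-a-5 puts 10 mg (or placebo) on Day 1 and then states: "On Day 3, the intervention and control group participants receive 30 mg of lorcaserin or placebo, respectively". The placebo arm follows the same testing schedule: "Both groups also will undergo assessments before and after administration of lorcaserin/placebo (identical to Day 1").

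Section 3-f gives the purpose of the two doses: "We selected two different one-time doses of the study drug to provide dose-response data". It also says that the 48-hour gap "was selected to provide time for the anticipated drug concentrations and muscle strength effects to return to baseline". A note to Table 3 lets the gap vary: "Day 3 may or may not be consecutive to day 2 depending on assessor availability".

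The primary analysis (7-a) compares 30 mg with control, and 7-b item 1 compares 10 mg with control, both by two-sample t-test. Item 4 is a pooled Emax analysis that names no day term. Only the sample-size text in 7-c makes clear that baseline and post-dose tests fall on one day. The same text assumes that the placebo group does not change.

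**The concern.** In the lorcaserin arm, dose and day move together. Let D be a patient's Day 3 change minus the Day 1 change, each change being post-dose minus pre-dose. The mean of D in that arm is the dose difference plus any difference between the days in the change that would have occurred without drug. A paired test on this arm cannot tell the two apart.

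If baseline is the same-day pre-dose value, a stable shift in strength level between the days cancels. What does not cancel is a day difference in the within-day change itself. The 48-hour gap is aimed at carry-over and does not address this. Because 7-b does not repeat the same-day definition, a Day 1 baseline is not ruled out there; under that reading, all recovery between the days would enter the comparison.

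At stake is how item 3 would be read. It is the one listed test set up directly as 10 mg against 30 mg, in a pilot meant to give preliminary data for a larger study. Without a caveat, a result made up of dose plus day could be carried forward as dose response.

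**Working it through.** **Inputs from 7-c.** 10 lorcaserin and 5 placebo patients; SD 9 kg; pre/post correlation r = 0.8; alpha 0.05 (taken as two-sided, since the plan does not say).

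**Assumptions not in the documents.** The correlation rho between a patient's Day 1 and Day 3 changes (0, 0.5 and 0.75 shown), and a day effect common to both arms (1 or 2 kg shown).

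**The plan's own figure.**
- SD of a same-day change = 9 × √(2 × (1 − 0.8)) = 5.69 kg.
- Detectable difference, normal approximation = (1.960 + 0.842) × 5.69 × √(1/10 + 1/5) = 8.73 kg. The exact t calculation gives 9.45 kg. The plan's figure of just over 9 kg is reproduced.
- At r = 0 the SD is 12.73 kg and the detectable difference is 19.53 kg, or 217% of the 9 kg baseline (21.13 kg, 235%, by exact t). The plan says 220%.
- The plan gives no figure for item 3.

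**The two estimates of the dose difference.**
- SD of D = 5.69 × √(2 × (1 − rho)).
- Paired: SE = SD of D / √10, 9 df, t = 2.262.
- Placebo-adjusted (mean D on lorcaserin minus mean D on placebo): SE = SD of D × √(1/10 + 1/5), 13 df, t = 2.160.
- SE ratio = √(0.3/0.1) = 1.73, whatever rho is.
- The adjusted estimate has the lower mean squared error once the day effect exceeds √(adjusted SE² − paired SE²).

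| | rho 0 | rho 0.5 | rho 0.75 |
|---|---|---|---|
| SD of D (kg) | 8.05 | 5.69 | 4.02 |
| Paired SE (kg) | 2.55 | 1.80 | 1.27 |
| Paired 95% half-width (kg) | 5.76 | 4.07 | 2.88 |
| Adjusted SE (kg) | 4.41 | 3.12 | 2.20 |
| Adjusted 95% half-width (kg) | 9.53 | 6.74 | 4.76 |
| Break-even day effect (kg) | 3.60 | 2.55 | 1.80 |
| Paired rejection, no dose difference, 1 kg day effect | 6.4% | 7.9% | 10.9% |
| Paired rejection, no dose difference, 2 kg day effect | 10.9% | 16.9% | 29.0% |

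In simulation at rho 0.5, the adjusted contrast averaged zero and rejected in about 5% of trials at day effects of 2 and 4.5 kg.

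**Power with no day effect, rho 0 to 0.5.** For a 9 kg increment: paired 88% to 99%, adjusted 47% to 76%. For 4.5 kg: paired 35% to 61%, adjusted 16% to 27%. The plan's 9 kg is a difference between 30 mg and placebo. It equals the increment from 10 to 30 mg only if 10 mg does nothing.

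**Placebo arm alone.** The half-width for mean D is 2.776 × SD of D / √5 = 10.0 kg (rho 0) or 7.1 kg (rho 0.5). Five patients can show only a large day effect.

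**Carry-over by half-life alone.** Section 4-a-6.11 states: "Lorcaserin has a plasma half-life of about 11 hours". At 48 hours, 0.5^(48/11) = 4.9% of the level remains.

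**The case against.** The strongest reply is that no day effect has been shown. The documents give no size or direction, and under the plan's own sizing assumption of no placebo change the day effect is zero and item 3 is valid. That stands. A reader might infer that Day 3 is favoured by practice, or that item 3 is biased. The documents do not support either. Day 1 need not be a patient's first strength test, because before enrolment "oral consent will be obtained to perform a brief (< 5 minute) in-bed assessment of muscle strength". The 1 to 2 kg shifts above are illustrations only.

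Second, the plan already holds most of the answer. If control changes are taken from the matching day and the same patients contribute on both days, the adjusted point estimate is simply the primary estimate minus the item 1 estimate. That also stands. What is missing is the interval for that difference, which needs within-patient D. On the same condition, the primary analysis and item 1 are not themselves affected by a day effect common to both arms.

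Third, the adjusted contrast is weak, so a reader might want it to replace the paired test, or to decide whether a dose response may be claimed. Neither is justified. An adjusted interval that includes zero shows imprecision; it does not show that dose and day are inseparable. Suppose a rule attached a disclaimer whenever that interval included zero. With no day effect at all and rho 0 to 0.5, simulation puts the disclaimer on about 61% to 67% of significant paired results for a true 4.5 kg increment, and on about 23% to 48% for 9 kg.

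Nor can it be said that the paired estimate is generally the closer one. At rho 0.75 and a 2 kg day effect its root mean squared error is √(1.27² + 2²) = 2.37 kg, against 2.20 kg for the adjusted estimate.

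**Conclusion.** The point holds as a statement about what item 3 estimates: dose plus any day difference in the same-day change, with no placebo-adjusted interval planned beside it. It is not a finding that item 3 is wrong or biased.

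The consequence is small for small day effects and grows with rho. At an assumed 1 kg the paired test rejects in 6% to 8% of trials with no dose difference, and at 2 kg in 11% to 17% (rho 0 to 0.5). Which estimate has the lower mean squared error depends on two unknowns, with break-even at 3.6, 2.5 and 1.8 kg for rho 0, 0.5 and 0.75. That is the reason to show both. All these figures rest on the plan's SD of 9 kg and r = 0.8, a day effect common to both arms, and complete data on 10 and 5 patients.

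This is a cheap improvement to one secondary analysis of a 15-patient pilot.

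**What to change.** Keep item 3 and add to 7-b:

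> Baseline is the same-day pre-dose value. Because dose order is fixed, the paired result estimates dose plus any day effect. Beside it we report the lorcaserin-minus-placebo difference in mean D, where D = (Day 3 post − Day 3 pre) − (Day 1 post − Day 1 pre), with a 95% confidence interval (two-sample t) and the number of patients with both dosing days in each arm.

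Do not make dose-response statements depend on the adjusted interval excluding zero.

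State the limits with the result. The contrast removes only a day effect common to both arms. It does not remove carry-over from the first active dose, or effects of unequal gaps when Day 3 is delayed.

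The cost is a few sentences and one extra estimate from data already scheduled, with no new visits or tests and no change to the primary analysis. The downside is that the report gains one imprecise secondary estimate.

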On Day 4, the intervention and control group participants will not receive any lorcaserin/placebo, but will undergo assessments (identical to Day 2).

4-a-6) Measurements

Participants will be monitored to ensure safety of lorcaserin/placebo administration. This monitoring will include a daily review of interim history (via chart review), medications, and laboratory values (details below), as well as assessment for changes in mental status and monitoring for serotonin syndrome (see table 3).

We also will obtain a battery of outcome measures to test the efficacy in improving muscle strength and assess the safety of lorcaserin, as described in tables 3.

All monitoring will be done by assessors blinded to group allocation.

Table 3: Safety and Efficacy Measures (numbers indicate the number of times within each study day that each measurement is performed)

Measurement	Number of assessments			
	Day 1*	Day 2†	Day 3***‡	Day 4†
Safety Measures				
Chart Review	1	1	1	1
Laboratory Tests (details below)	1	1	1	1
EKG	2	1	1	1
RASS sedation score	2***	1	2***	1
CAM-ICU delirium screen	2***	1	2***	1
Neuro Psychiatric Screen	2	1	1	1
Hunter Serotonin Toxicity Criteria	1	1	1	1

Efficacy Measures				
Handgrip Strength (Primary Outcome)	2***	1	2***	1
Arm & leg strength (MMT using MRC Scale)	2***	1	2***	1
Quadriceps Strength using handheld dynamometry	2***	1	2***	1
Lorcaserin serum drug levels [‡]	1	1	1	1
Electromyography & Nerve Conduction Study	once only to assess for any peripheral neuromyopathy****			

MMT: Manual muscle strength testing; MRC: Medical Research Council; HHD: Hand-Held Dynamometry; EKG: Electrocardiogram; RASS: Richmond Agitation Sedation Scale; NPI-C: Neuropsychiatric Inventory - Clinician Rating Scale; CAM-ICU: Confusion Assessment Method for the ICU; Hunter Criteria: will be used to evaluate patients for serotonin syndrome (24)

* 10 mg of lorcaserin or placebo administered

** 30 mg of lorcaserin or placebo administered

*** measures are performed as close to the time as drug or placebo administration as possible (within 4 hours) and as soon as possible (between 2 - 6 hours) after drug or placebo administration, on Days 1 and 3 only

**** EMG & NCS will be performed at any time point after the patient is randomized into study, and will be used to help interpret the results of strength tests

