11. Unable to receive, or unlikely to absorb, study drug (e.g. bowel obstruction, ischemia, or infarction; short gut syndrome)
12. Body mass index $>$ 40
13. Patient not expected to survive $>$ 4 days
14. Pregnancy (based on urine or blood test results based on standard practice in the subject's ICU) or lactation
15. Allergy to lorcaserin or lorcaserin taken in the prior 7 days
16. Enrolled in another interventional drug or physical rehabilitation trial
17. Physician declines for patient to be enrolled
18. Patient or proxy declines consent
19. Unable to reach proxy for consent
20. Non-English speaking

6) Drugs/ Substances/ Devices

6-a) The rationale for choosing the drug and dose or for choosing the device to be used.

It is known that activation of serotonin receptors (5-HT_{2C}) in the spinal cord increases persistent inward sodium current to allow motor neurons to fire repetitively, and lorcaserin, as a selective 5-HT_{2C} agonist was used successfully in rat models (see Background, section 3-d)

The lorcaserin dose that normalizes motor neuron firing in rats is 3 mg/kg. The human dose for weight loss is 10 mg PO twice daily, but doses up to 60 mg were tolerated in clinical trials. Based on rat-to-human allometric scaling of both pharmacokinetic parameters and 5-HT_{2C} receptor sensitivity (EC₅₀), the 3 mg/kg dose in a rat is

Date: 1 August 2016

Principal Investigator: [name] PhD

Application Number: IRB00072940

0.26 mg/kg or 18 mg in a 70 kg adult. Based on doses of lorcaserin that were given to patients prior to FDA approval and rat to human allometric scaling, it appears that treatment of patients with effective doses of lorcaserin is feasible (See Background, section 3-e)

6-b) Justification and safety information if FDA approved drugs will be administered for non-FDA approved indications or if doses or routes of administration or participant populations are changed.

See attached IND Exemption document

6-c) Justification and safety information if non-FDA approved drugs without an IND will be administered.

Not Applicable

7) Study Statistics

7-a) Primary outcome variable.

The primary analysis will compare the mean change in hand grip strength from baseline to post-drug testing across the 30 mg intervention dose vs. control group using a two-sample t-test.

7-b) Secondary outcome variables.

Secondary analyses will include the following:

- 1) replication of the primary analysis for the 10 mg intervention dose vs. control group,

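### Section 7-b item 4 pools repeated strength measures in one Emax fit with no stated patient effect, so some standard errors would be wrong (direction varies by parameter) and precision is lost

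*Combined protocol and SAP*

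**What the plan says.** Section 7-b item 4 is "a PK-PD analysis for all concentration-strength measures for all observations (across the 4 days"), fitted "using a traditional Emax model pooling all subjects and all time points". The response named is strength, whereas section 7-a and items 1 to 3 of 7-b all use change from baseline. No section adds a patient effect, a clustered variance, a mixed model or a subject-level interval to item 4.

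Section 7-c gives 10 lorcaserin and 5 placebo patients and a grip strength mean (SD) of 9 (9) kg. On the repeat measures it states: "This calculation assumes that the baseline and post-drug testing measures would be highly correlated", with r = 0.8. That figure refers to pre- and post-drug testing on one day. The same section says the sample "is a convenience sample to establish preliminary data for a potential larger future study".

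Table 3 in section 4-a-6, where "numbers indicate the number of times within each study day that each measurement is performed", gives grip strength 2, 1, 2, 1 on Days 1 to 4 and one serum level per day. On sampling times, section 4-a-6.11 says: "Lorcaserin has a plasma half-life of about 11 hours, and trough concentration samples will be collected at approximately two half-lives". A Table 3 footnote adds: "Day 3 may or may not be consecutive to day 2 depending on assessor availability".

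**The concern.** At SD 9 kg and r = 0.8, 80% of the variance in grip strength lies between patients. A fit that ignores which patient a value came from treats that variance as independent residual noise. Two things follow. Standard errors computed as if observations were independent are wrong. And the within-patient comparison, which carries most of the information about the drug, is not used.

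At stake are the concentration-effect estimates, which form part of the preliminary data this pilot is meant to hand on. If placebo patients enter, the intervals around baseline strength and around the effects at the two dose peaks would look tighter than they are.

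**Working it through.** **1. The plan's own figure.** SD of change = 9 × √(2(1 − r)). At r = 0.8 this is 5.69 kg. Detectable difference, normal approximation, two-sided: (1.96 + 0.84) × 5.69 × √(1/10 + 1/5) = 8.73 kg, or 97% of 9 kg, matching the stated 9 kg. At r = 0 the SD is 12.73 kg and the difference 19.53 kg (217%), matching the stated 220%. So r = 0.8 is the working assumption and r = 0 the plan's worst case.

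**2. Pairs per patient.**
- Four pairs are measured, one serum level per day.
- A fifth comes from pairing Day 1 pre-dose strength with zero concentration. Exclusion 15 ("Allergy to lorcaserin or lorcaserin taken in the prior 7 days") allows this: 168 h / 11 h is about 15 half-lives.
- A sixth needs a calculated Day 3 pre-dose concentration: at 48 h, 46 h after a 2 h peak, 2^(−46/11) is about 6% of the 10 mg peak.

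**3. Limits by hand.** With m values per patient and common correlation r, a purely between-patient quantity has nominal/true SE = 1/√(1 + (m − 1)r). At r = 0.8 this is 0.54, 0.49 and 0.45 for m = 4, 5 and 6. A purely within-patient contrast has 1/√(1 − r) = 2.24. Each parameter falls between these limits, according to how much of its information is between patients. Placebo patients inform only E0, which pushes it towards the lower limit.

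**4. The Emax fit.** Model: strength = E0 + Emax·C/(EC50 + C), all three estimated. Nominal variance is σ²(X′X)⁻¹. True variance is (X′X)⁻¹X′VX(X′X)⁻¹, where V has variance 81 and within-patient correlation 0.8. Assumptions not in the documents: r = 0.8 on all days, dose-proportional concentrations with 30% variation between patients, EC50 0.3 to 3 times the 10 mg peak, true 30 mg effect 9 kg.

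| Nominal/true SE | Placebo in, 4 to 6 pairs |
|---|---|
| E0 | 0.49 to 0.58 |
| Effect at 10 mg peak | 0.53 to 0.73 |
| Effect at 30 mg peak | 0.66 to 0.97 |
| EC50 | 0.85 to 1.23 |
| Emax | 0.88 to 1.60 |

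Example at EC50 1.8, five pairs, nominal against true: E0 1.4 vs 2.6 kg, 10 mg effect 2.4 vs 3.6 kg, 30 mg effect 2.9 vs 3.4 kg, Emax 10.8 vs 7.4 kg.

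With lorcaserin patients only, the ratios are 1.35 to 2.2, except E0 with five pairs (0.86 to 0.97) or six (0.71 to 0.88).

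**5. Coverage.** A ratio of 0.5 implies coverage of 2Φ(1.96 × 0.5) − 1 = 67% for a nominal 95% interval; 0.7 implies 83%. Simulated nonlinear pooled fits with placebo in agree: E0 65% to 72%; 10 mg effect 70% to 77%, 79% to 85% and 76% to 85% with 4, 5 and 6 pairs; 30 mg effect 79% to 83%, 88% to 91% and 88% to 92%.

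**6. Precision of the 30 mg effect, placebo in (simulated SD, kg).**

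| Pairs | Pooled | Subject effect |
|---|---|---|
| 4 | 4.7 to 5.1 | 2.5 to 3.9 |
| 5 | 3.4 to 3.8 | 1.5 to 1.7 |
| 6 | 3.1 to 3.4 | 1.4 to 1.5 |

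With five pairs the loss is at least 1 − 1.7/3.4 = 50%. With four pairs it runs from 1 − 3.9/4.7 = 17% to 1 − 2.5/5.1 = 51%. The linearised calculation gives about 11% (4.5 vs 4.0 kg, low EC50) to 45%.

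**7. Other correlations.** At EC50 1.8, pooled coverage of the 30 mg effect with 4, 5 and 6 pairs is 89%, 92% and 94% if correlation fades by a factor of 0.8 per day; 93% each at r = 0.4; and 95% to 97% at r = 0.

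**8. Is a subject effect alone enough?** Patients are recovering and 10 mg always precedes 30 mg. With an assumed recovery of 1 kg/day and five pairs, a subject-effect model without a day term overstates the 30 mg effect by about 1.5 to 1.6 kg, roughly one SE. The pooled fit is biased by 0.9 to 1.0 kg. A linear day term removes this bias and raises the SE from about 1.6 to 1.7 kg to about 1.8 kg.

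**The case against.** The strongest reply is that item 4 is underspecified rather than wrong. It does not say that observations are treated as independent, which response scale is used, or that intervals will be reported. That is fair: the missing patient effect is inferred from the pooling and from the silence elsewhere. The figures above apply to strength levels, not to a change-score fit.

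Four further points stand in part.
- r = 0.8 is stated only for same-day measures, and Day 3 need not directly follow Day 2. Carrying it across days is an extrapolation, and step 7 shows the error shrinking without it.
- The clearest understatement falls on E0 and the peak effects, which item 4 does not list. Section 7-a and items 1 and 3 of 7-b already estimate dose effects from within-patient change.
- Peak serum is drawn at 2 or 3 h and post-dose strength is tested at 2 to 6 h. The measured pairs are therefore not simultaneous, and the calculations make no allowance for this.
- Pooling is simple, and a mixed model may fail in 15 patients. In the simulations, however, EC50 reached the search limit less often with a subject effect (1% to 9% against 11% to 26% pooled, five pairs; 7% to 17% against 17% to 32%, four pairs).

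None of this supplies a reason to leave the patient out of the model.

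**Conclusion.** The point holds in limited form. If r = 0.8 carries across days and placebo patients enter as strength levels, nominal SEs are too small for E0 (about 0.5 to 0.6 of the true value), the 10 mg effect (about 0.5 to 0.7) and the 30 mg effect (about 0.7 to 0.95), and roughly right or too large for EC50 and Emax. With lorcaserin patients only they are mostly too large.

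A reader might infer three stronger things that the documents do not support.
- That every interval would be too narrow: the direction depends on the parameter and on who enters, and at r = 0, the plan's own worst case, there is no error.
- That pooling always throws away half the precision: this is so with five or six pairs, but with the four measured pairs the loss is about 10% to 50%, depending on EC50.
- That the trial's main result is at risk: item 4 is a secondary analysis with no named test, in a convenience-sample pilot, and the primary t-test uses each patient's change.

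**What to change.** In section 7-b item 4, replace the pooled fit with strength = E0_i + day effect + Emax·C/(EC50 + C), specified as follows.
- A subject random effect on E0.
- A day term, linear or by study day, estimated from all patients, with placebo patients at concentration zero.
- Intervals that are subject-clustered with a small-sample correction, or from a subject-level bootstrap.
- Data: the four measured pairs plus Day 1 pre-dose strength at concentration zero. Omit the lorcaserin patients' Day 3 pre-dose strength, or state how its concentration is calculated.
- Record the actual times of serum sampling and strength testing, and note that they are not simultaneous.
- If EC50 does not converge, report it as not estimable and fit the same subject-effect and day-term model with a linear concentration term.

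Without a day term, such a model with corrected cluster intervals covered the 30 mg effect in 92% to 95% (four pairs), 94% to 95% (five) and 93% to 94% (six) of simulated trials with placebo in. The day-term version was checked for SE and bias only, and the linear fallback was not simulated.

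The cost is a few sentences and a different fitting routine, with no new patients or samples. The downsides are possible non-convergence in 15 patients and the slightly larger SE from the day term.
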